6.2 STUDY INTERVENTION COMPLIANCE

Adherence to the protocol regarding the study intervention will be assessed through the monitoring of critical processes as detailed in the Data and Safety Monitoring Plan (DSMP).

- Site procedure for maintaining accurate link of infant with study ID number
- Site procedure to ensure correct labeling of blood/DNA sample(s)
- Accurate and relevant Human Phenotype Ontology terms and clinical information submitted by the enrolling site to the laboratory for use in analysis of variants with phenotype
- Laboratory protocols adhering to CLIA/CAP/state guidelines
- Laboratory procedures for accurate matching of a result with the infant
- Laboratory procedures to ensure any secondary findings for the infant are only reported if the criteria pertaining to the infant as outlined in section 6.1.1 are met
- Laboratory procedures to ensure secondary findings for a biological parent are only reported if the criteria pertaining to a parent as outlined in section 6.1.1 are met
- Confirmation testing completed prior to reporting of pathogenic, likely pathogenic, or suspicious VUS results or the documentation of a provisional result exception
- Accurate dissemination of the report of results from the laboratories to the infant's EMR

6.3 CONCOMITANT THERAPY

There are no restrictions on concomitant medications, treatments or procedures allowed during the study. Medications and procedures will be captured during data collection.

7 STUDY INTERVENTION DISCONTINUATION AND PARTICIPANT DISCONTINUATION/ WITHDRAWAL

7.1 DISCONTINUATION OF STUDY INTERVENTION

The study intervention is diagnostic tests. Discontinuation of the study intervention might occur if a clinical diagnosis is determined prior to the completion of NewbornDx or rWGS. In this case, the infant will be withdrawn from the study per section 7.2.

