5 STUDY POPULATION

5.1 INCLUSION CRITERIA

In order to be eligible to participate in this study, an infant must meet all of the following criteria:

1. Documented informed consent from the parent/guardian
2. Signs/symptoms consistent with a possible genetic disorder including, but not limited to dysmorphic features, congenital anomalies, hypotonia, seizures, clotting, poor oral feeding skills
3. Admitted to a hospital (NICU, PICU, CVICU, inpatient floor) participating in this study at the time of enrollment (enrollment is not limited to the initial hospitalization after birth, it may occur during a readmission)
4. Less than one year CGA

There is not a requirement for clinical genetic testing prior to enrollment. However, enrollment in this study is not intended to replace targeted available genetic testing for specific suspected disorders that match the phenotype of the infant and make rWGS testing unnecessary. Examples include trisomies or a high likelihood of DiGeorge syndrome. In these cases, targeted genetic testing for a suspected disorder should be done prior to enrollment (e.g. DiGeorge syndrome and FISH for 22q11.2 deletion). Clinical genetic testing does not need to be completed prior to enrollment if there is more than one diagnosis on the differential diagnosis list. Other than these few situations, our goal should be to understand the role of utilizing rWGS and NewbornDx as a first line choice of testing.

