5.3 SCREEN FAILURES

Screen failures are defined as infants whose parent(s) consent to participation in the clinical trial but who do not have NewbornDx or rWGS performed. This could occur if a clinical diagnosis was determined after consent was obtained but prior to the start of any study procedures (section 7 addresses the procedure for subject withdrawal if a clinical diagnosis is determined after study procedures commence but before the completion of genomic sequencing). A minimal set of screen failure information will be collected including demography, screen failure details and eligibility criteria.

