7.2 PARTICIPANT DISCONTINUATION/WITHDRAWAL FROM THE STUDY

An infant's parent/guardian or a biological parent can withdraw their own participation at any time and is not obligated to state the reason for withdrawal. However, the investigator should make a reasonable effort to ascertain the reason for withdrawal while fully respecting the parent/guardian's or biological parents' rights.

An investigator may discontinue or withdraw an infant from the study for the following reasons:

- A clinical diagnosis was determined prior to completing the genomic testing for the infant
- Withdrawal is requested by the NIH or DSMB
- If the infant meets an exclusion criterion (either newly developed or not previously recognized) that precludes further study participation (i.e. CMV testing that came back positive after enrollment)
- If the blood samples cannot be safely obtained from the infant
- The parent/guardian withdraws consent for the infant

The reason for discontinuation of the infant or biological parent will be recorded in the study database. An infant for whom the parent/guardian provided consent but who does not receive the study intervention may be replaced. An infant for whom the parent/guardian provided consent and who received the study intervention and was subsequently withdrawn from the study will not be replaced.

In the event of an infant death prior to the completion of genetic testing, the testing will continue to be done unless the parent/guardian indicates otherwise. There is a potential to provide information regarding a hereditary disorder for future children.

If an infant is withdrawn from the study, the data already collected on the infant may be used unless the parent/guardian indicates otherwise in writing.

The following actions will be taken at the local study site and laboratories as applicable after receiving a request to withdraw:

- Upon receipt of request to withdraw, the enrolling site will notify RCIGM and Athena (Quest) of withdrawal of the infant and/or the biological parent(s). Mount Sinai will also notify Sema4.

- The enrolling site or laboratories that are in possession of unused blood from the infant and/or the biological parent(s) will ensure blood samples are destroyed.
- Isolated DNA will be destroyed. The laboratories will permanently break any link between personal identifying information and sequencing data files from the infant and/or the biological parent(s).

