9.3 POPULATIONS FOR ANALYSES

- ICF Dataset: All families who were approached for study participation
- Intention-to-Treat (ITT) Dataset: all consented infants
- Modified Intention-to-Treat Dataset: all consented infants for whom both NewbornDx and rWGS genomic sequencing results were returned
- Per-Protocol Dataset: all consented infants who received both NewbornDx and rWGS (modified intention-to-treat dataset) and completed the study period for the analysis of the primary and secondary objectives without clinically important protocol deviations. Clinically important protocol deviations will be identified and documented prior to the database lock.
- Time to Molecular Diagnosis Dataset: The Modified Intention-to-Treat Analysis Dataset excluding the infants who did not have a confirmed positive result
- Urgent Testing Dataset: All infants who required urgent testing per section 8.1

- Safety Analysis Dataset: All infants for whom blood specimens were obtained or data collected

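### Infants clinically diagnosed before both tests finish can be withdrawn and so leave both primary yields, and no sensitivity analysis of the yields is planned

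*Combined protocol and SAP*

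**What the plan says.** Section 7.1 says that testing might be discontinued if a clinical diagnosis comes before NewbornDx or rWGS is complete, and continues: "In this case, the infant will be withdrawn from the study per section 7.2". Section 7.2 lists the same trigger, "A clinical diagnosis was determined prior to completing the genomic testing for the infant", under a permissive heading: "An investigator may discontinue or withdraw an infant from the study for the following reasons". Section 5.3 sends to section 7 the case where the diagnosis comes after sampling has begun: "if a clinical diagnosis is determined after study procedures commence but before the completion of genomic sequencing". After withdrawal, "the data already collected on the infant may be used unless the parent/guardian indicates otherwise in writing". The steps that follow a request to withdraw include "Isolated DNA will be destroyed".

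Section 9.3 defines the mITT set as "all consented infants for whom both NewbornDx and rWGS genomic sequencing results were returned". The endpoint table in 9.4.2 assigns both primary yields to that set. Section 9.3 also defines an ITT set of all consented infants, but no row of the 9.4.2 table uses it. Section 9.4.1 describes the yields as proportions of enrolled infants.

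The plan foresees the group concerned. Section 9.4.1 expects some SOC diagnoses after enrollment and plans the proportion, with a 95% CI, of infants diagnosed by SOC before genomic results are available. Section 5.1 allows enrollment with clinical tests pending: "Clinical genetic testing does not need to be completed prior to enrollment if there is more than one diagnosis on the differential diagnosis list".

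**The concern.** Whether an infant stays in the yield depends partly on having received a diagnosis, which is close to the outcome itself. Two infants diagnosed by SOC in the same week are treated differently if one has both sequencing results returned and the other is withdrawn with one outstanding. The second leaves both denominators, even for a test that had already finished and whose data section 7.2 allows to be used.

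The mITT yield therefore describes neither all enrolled infants nor only those whom SOC could not diagnose. Section 5.1 states the aim of understanding the two tests as a first-line choice, and infants whom SOC diagnoses quickly belong to that population. Because the plan is descriptive (9.1), the estimates and their intervals are the whole primary result, so what is at stake is what they can be said to estimate.

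**Working it through.** **1. The plan's own precision figure.** Section 9.2 assumes 400 completed infants. The Wald interval is p ± z·√(p(1−p)/400). At p = 0.50 and z = 1.96 the half-width is 1.96 × 0.025 = 0.049, giving 0.451 to 0.549, which matches the stated 0.45 to 0.55. All six rows of the table reproduce with z = 2. With z = 1.96 only the 0.30 row differs, by 0.01 at each limit, which is rounding. The full width at p = 0.50 is 2 × 0.049 = 0.098.

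**2. Inputs for the check.** Expected yield: 40% to 60% (9.2). Withdrawn share f: not given anywhere, so 2%, 5% and 10% are **assumptions**. The only SOC diagnosis rate in the documents is 15% over the neonatal period in another study (2.1), so 10% is an upper-end case.

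**3. Direction.** Let p be the mITT yield and s the share of withdrawn infants that the test would have detected. The yield with those infants put back is (1−f)·p + f·s, which differs from p by f·(s−p). It is zero if s = p, positive if s > p (mITT understates) and negative if s < p (mITT overstates). Either is possible: sequencing may find most disorders that SOC finds, but a clinical diagnosis need not be molecular, and section 2.3.1 expects some causal structural variants to be missed. At p = 0.50 and s = 0.80 the difference is f × 0.30, that is 0.6, 1.5 or 3.0 points at 2%, 5% or 10%.

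**4. Bounds (s = 0 and s = 1).** Lower (1−f)·p; upper (1−f)·p + f; width f.

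| mITT yield | 2% withdrawn | 5% | 10% |
|---|---|---|---|
| 40% | 39.2 to 41.2% | 38.0 to 43.0% | 36.0 to 46.0% |
| 50% | 49.0 to 51.0% | 47.5 to 52.5% | 45.0 to 55.0% |
| 60% | 58.8 to 60.8% | 57.0 to 62.0% | 54.0 to 64.0% |

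Setting the width f equal to the full CI width of 0.098 gives f = 9.8%: about 39 of 400 infants, or 400/0.902 − 400 ≈ 43 withdrawn on top of 400 completers. A single result already generated would narrow the bounds for that test.

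**5. Bounds with sampling error.** Take 400 infants in all and p = 0.50. Subtract 1.96·√(q(1−q)/400) from the lower bound and add it to the upper, with q the bound. The result is 44.1 to 55.9% at 2%, 42.6 to 57.4% at 5% and 40.1 to 59.9% at 10%. The mITT interval with 380 infants is 45.0 to 55.0%.

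**6. Ratio of yields.** Assume that rWGS finds whatever NewbornDx finds. With k withdrawn of 400, w = 0.5·(400−k) rWGS positives and observed ratio R, the lower bound is R·w/(w+k) (all withdrawn found by rWGS only) and the upper is (R·w+k)/(w+k) (all found by both). For R = 0.75:
- k = 8, w = 196: 147/204 = 0.72 to 155/204 = 0.76
- k = 20, w = 190: 142.5/210 = 0.68 to 162.5/210 = 0.77
- k = 40, w = 180: 135/220 = 0.61 to 175/220 = 0.80

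**The case against.** **The primary set is fixed.** The 9.4.2 table names mITT for both yields, and a specific endpoint table normally governs general wording. A both-results set is also natural for a paired ratio. This stands: a reader might infer that the plan leaves the denominator open, but the fault is a mismatch of wording in 9.4.1.

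**Withdrawal is already discretionary.** Section 7.1 says discontinuation might occur, and 7.2 says the investigator may withdraw. A reader could take the second sentence of 7.1 as a requirement, but the two sections together do not establish one. The two should agree, because differing site practice would decide who is counted.

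**The exclusion suits the objective.** Section 3 concerns disorders of unknown cause, and 5.2 excludes a known genetic diagnosis. This supports a narrower target, but SOC-first infants whose tests finished would then need separating too, and the plan does not do that for the yields.

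**Related analyses are planned.** Withdrawal reasons are recorded (7.2), and an SOC-first proportion is planned, though with no dataset named; if it is computed in mITT, the withdrawn infants vanish from it too. The Kaplan-Meier contrast in 9.4.1, which includes all enrolled infants and excludes those diagnosed first by SOC, covers time to diagnosis, not yield.

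**The effect may be small.** The window before results is short compared with the neonatal period behind the 15% figure, and 5.1 sends obvious disorders for targeted testing before enrollment. This stands.

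**Conclusion.** The point holds as a cheap improvement to the plan. Sections 7.1 and 7.2 allow an outcome-related group to leave both primary yields, SOC-first infants with completed tests remain, and nothing planned shows how much this matters. At an mITT yield of 50% the possible shift is 1 point either way with 2% withdrawn, 2.5 with 5%, and 5 with 10%. Every withdrawn share is an assumption, and the bounds take the extremes of none or all detected.

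A reader might infer more: that the primary yields are biased in a known direction, or that their 95% intervals fail to cover. The documents support neither. The direction turns on s − p, which they do not give. The mITT interval is a valid interval for the mITT yield; it would undercover only against an all-infant target that the plan does not assign to the yields. Nor would a lower ratio bound below the 60% of Hypothesis #1 trigger a decision, since 9.1 rules out hypothesis testing. Loss of the chance to test later is likewise conditional: DNA destruction in 7.2 follows a request to withdraw, and whether that includes withdrawal by the investigator is not stated.

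**What to change.** - Keep mITT as the primary set and align the wording of 9.4.1 to it.
- Base the SOC-first proportion on all consented infants, and report the number withdrawn because of a clinical diagnosis.
- Report both yields and their ratio with and without SOC-first infants.
- Add best- and worst-case bounds that include those withdrawn, using any single result already generated.
- State in 7.1, consistently with 7.2, that a clinical diagnosis alone does not require withdrawal and that tests already under way may finish if the family agrees. New sequencing of an infant whose diagnosis is known need not be mandated.

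The cost is a few sentences, a little more analysis, wider stated bounds, and a small laboratory cost in a few infants. Section 2.1 puts a clinical rWGS trio at about $19,500; finishing one already started should cost less. The family's agreement matters because the risk of secondary findings remains.

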7.2 PARTICIPANT DISCONTINUATION/WITHDRAWAL FROM THE STUDY

An infant's parent/guardian or a biological parent can withdraw their own participation at any time and is not obligated to state the reason for withdrawal. However, the investigator should make a reasonable effort to ascertain the reason for withdrawal while fully respecting the parent/guardian's or biological parents' rights.

An investigator may discontinue or withdraw an infant from the study for the following reasons:

- A clinical diagnosis was determined prior to completing the genomic testing for the infant
- Withdrawal is requested by the NIH or DSMB
- If the infant meets an exclusion criterion (either newly developed or not previously recognized) that precludes further study participation (i.e. CMV testing that came back positive after enrollment)
- If the blood samples cannot be safely obtained from the infant
- The parent/guardian withdraws consent for the infant

The reason for discontinuation of the infant or biological parent will be recorded in the study database. An infant for whom the parent/guardian provided consent but who does not receive the study intervention may be replaced. An infant for whom the parent/guardian provided consent and who received the study intervention and was subsequently withdrawn from the study will not be replaced.

In the event of an infant death prior to the completion of genetic testing, the testing will continue to be done unless the parent/guardian indicates otherwise. There is a potential to provide information regarding a hereditary disorder for future children.

If an infant is withdrawn from the study, the data already collected on the infant may be used unless the parent/guardian indicates otherwise in writing.

The following actions will be taken at the local study site and laboratories as applicable after receiving a request to withdraw:

- Upon receipt of request to withdraw, the enrolling site will notify RCIGM and Athena (Quest) of withdrawal of the infant and/or the biological parent(s). Mount Sinai will also notify Sema4.

- The enrolling site or laboratories that are in possession of unused blood from the infant and/or the biological parent(s) will ensure blood samples are destroyed.
- Isolated DNA will be destroyed. The laboratories will permanently break any link between personal identifying information and sequencing data files from the infant and/or the biological parent(s).
- The RCIGM laboratory will remove the REDCap Infant Study ID from its ordering portal.
- If a back-up of the inventory database/informatics system is ever restored, then the laboratory should ensure that the relevant identifying records stored on the discarded samples log are again deleted from the records.
- The enrolling site must document reasons for withdrawal and record it in the REDCap database.
- The enrolling site will permanently break any link between personal identifying information and the anonymized records and data in REDCap by replacing protected health information (PHI) in the Master List of enrolled subject and REDCap Study Infant ID with a note that the infant has withdrawn.
- The enrolling site and laboratories must shred any hard copies of associated identifying information not required to be maintained for regulatory purposes.
- The enrolling site must retain the executed consent form and request for withdrawal in a separate, secure file of discontinued infants and redact any identifiers that link the infant to the data (such as infant's study ID number).
- The laboratories will certify that identifying links have been broken and as applicable, that biological material has been destroyed.
- Only anonymous data may be used for future research after consent has been revoked.

7.3 LOST TO FOLLOW-UP

An infant will be considered lost to follow-up if the enrolling site is unable to contact a parent/guardian at the time the infant turns 1 year CGA plus 2 months. In order to reduce the risk of lost to follow-up, study staff will have the parent/guardian(s) provide several methods of contact for themselves as well as a family member or friend who would know how to reach them if their contact information changed or are unreachable (refer to Follow-up Contact Information form). The enrolling site will attempt to contact the parent/guardian(s) monthly. Before an infant is deemed lost to follow-up, the enrolling site will make every effort to regain contact with the infant (multiple contacts and, if necessary, a certified letter to the infant's last known mailing address or local equivalent methods). These contact attempts should be documented in the infant's study file. If the infant continues to be unreachable, he or she will be considered to have withdrawn from the study with a primary reason of lost to follow-up. It is permissible to contact the infant's primary care provider to obtain relevant information on the condition of the infant if the parent/guardian(s) are not available and they have given permission by signing the ICF and/or medical record release form.

8 STUDY ASSESSMENTS AND PROCEDURES

8.1 SCREENING & INFORMED CONSENT

Screening

Infants born with a suspected genetic disorder will be screened for all inclusion/exclusion criteria. Potential infants will be identified by study personnel reviewing the daily census of applicable hospital locations and relevant medical records or by the clinical team. Study or clinical personnel will identify potential candidates based on the primary diagnosis, signs/symptoms, and CGA. The study team will discuss eligibility of the infant with the attending physician of record and if in agreement, the family will be approached for the study.

There is not a limit to how many infants can be enrolled at any one site. Infants who are already an inpatient at the time a site opens for enrollment may be approached for this study if they fulfill the inclusion/exclusion criteria. Those infants identified through the screening process will have the following data recorded on the Screening Log and/or entered into REDCap. The Infant Study ID will be used to code screening data and is generated by REDCap consisting of a 4-digit number (1-digit site number and a 3-digit infant number).

Category	Information from the medical record which may be recorded on a paper or electronic screening log kept securely at the enrolling site	Screening data that will be entered into REDCap if the infant is approached for study participation regardless of consent status
Identifying Information	name, date of birth, medical record number	N/A
Screening Process	screening ID, date screened, location in hospital, whether or not the infant is eligible, if the family was approached for consent, date of approach, reason why an eligible infant was not approached	screening ID
Clinical Information	gestational age at birth, age at time of screening, clinical signs/symptoms and primary system involvement, clinical differential diagnosis, prenatal and postnatal clinical genetic testing and newborn screening results, list of genetic tests	gestational age at birth, age at time of screening, primary system(s) involvement related to patient nomination, sex of infant

	pending, newborn screening test results, sex of infant	
Consent Process	languages used during the consent process; if telephone consent was used; if clinical genetics was involved prior to the consent process; enrollment status; reason for declining study if voluntarily given	languages used during the consent process; if telephone consent was used; if clinical genetics was involved prior to the consent process; enrollment status; reason for declining study if voluntarily given
Demographics	type of health insurance, race and ethnicity of the biological mother and biological father (in order to represent the infant)	type of health insurance, race and ethnicity of the biological mother and biological father, 5-digit zip code

Identifying information from the screening log will be destroyed at the end of the study.

Note: for screened patients that have already been entered into REDCap under the current HIPAA authorization waiver by the IRB, we will first delete the primary signs/symptoms already captured in the database and then add the primary system involvement and zip code. The purpose of removing primary signs/symptoms and replacing it with system involvement is to reduce the risk of identification due to unique features once zip code is added.

Informed Consent

Consent by one parent/guardian is required for participation by the infant. Each biological parent will give permission to obtain and use his or her own blood sample and elect parental secondary findings. Written documentation of informed consent from the parent/guardian and/or biological parent(s) must be documented prior to the conduct of any study procedures. Refer to section 10.1.1 Process of Informed Consent.

If the parent/guardian provides consent for the infant to participate, study personnel at the enrolling site will:

- Review the ICF and ensure that it is properly completed
- Review whether or not the parent/guardian opted-in to receive secondary findings for the infant
- Review whether or not the biological parent(s) opted-in to receive secondary findings for themselves
- Provide the parent/guardian and the biological parents, as applicable, with a copy of the signed ICF
- Notify the attending physician of record of the parent/guardian's decision to participate
- Record that consent was obtained in the infant's medical record
- Place a copy of the signed ICF into the infant's medical record
- File the original signed ICF in the research file

- Complete screening log and the Demographics, Symptoms and Consent eCRFs in REDCap

If the parent/guardian refuses participation for the infant, study personnel will:

- Communicate refusal to relevant study or clinical personnel
- Complete screening log and the Demographics, Symptoms and Consent eCRFs in REDCap

